use treatment.)^{61,62,63} There is a growing need in treatment interventions of co-occurring PTSD and AUD but the current literature provides inconclusive and contradictory results of various pharmacologic treatments.^{64,65} The interaction of PTSD symptoms with active naltrexone alcohol treatment is one that is not well known or studied.⁶⁶ We will pilot in all remaining new patients and existing active patients validated brief screeners for trauma history and PTSD symptoms for estimations of prevalence and changes over time during active NTX treatment of alcohol use disorders.

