3.9 Investigative Team Roles and Study Management

[name] as PI will oversee all aspects of the study. As detailed in the Budget Justification, each Key Personnel will perform specific and distinct roles. Our economic analysis team will plan and analyze the cost-effectiveness components. [name] along with our study statistician will conduct the analyses of the primary and secondary effectiveness outcomes, based on the dataset collected and managed by our data managers. Our team will also include co-investigators who will serve as study physicians and assist in all aspects of study conduct. [name], a senior mentor to [name] and Director of the NIDA CTN NY Node, will serve as a co-investigator and assist with all aspects of the study in a senior advisory role. [name] and [name], consultants, will assist with CDT analysis, COMBINE MM implementation and OPRM1 genomic analysis.

[name] will be in daily contact with the Program Manager, Project Manager, Research Coordinators, and study clinicians. Weekly meetings will bring together core staff to trouble-shoot study implementation and daily management. Monthly conference calls will bring together all of the key personnel and, as needed, the two consultants, to discuss study conduct and eventual analysis and manuscript preparation. Separately, [name] will meet monthly or more frequently, depending on the study phase, with the study statistician and data manager regarding data management and analysis.

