9.0 Power and Sample Size

As in the original proposal and based on our recent feasibility study of XR-NTX in primary care² and the O-NTX treatment retention and adherence literature,^{6,7,19} including the single review by Roozen comparing the two medications,²⁸ we are powering this study on the assumption that XR-NTX is approximately twice as effective as O-NTX at achieving drinking reductions, including a good clinical outcome of abstinence or moderate-drinking-only during weeks 5-24, and also increased days abstinent and reduced rates of heavy drinking, drinks per drinking day, and drinks per day overall. This is

hypothesized to be mediated by superior naltrexone adherence. We predict based on our pilot data and the literature that 40-50% of patients will complete 24 weeks of treatment on XR-NTX, compared to <20% on O-NTX, based on O-NTX clinical trial and commercial refill data. We then estimate rates of the primary good clinical outcome of approximately 20% in O-NTX participants and 40% in the XR-NTX arm, roughly the same as adherence rates. This is based on our pilot data, in which 36 of 40 persons completing 12 weeks of XR-NTX qualified for the moderate-drinking-only good clinical outcome, and COMBINE, in which adherent oral naltrexone/MM patients reported high rates of the same moderate-drinking-only good clinical outcome during the final 8 of 16 weeks of the study. With 100 subjects per group, we anticipate power of 0.84 to detect a 20% absolute difference in the primary outcome based on the Fisher's exact test. These projected rates, however, are not well established, nor based on large datasets of heterogeneous alcohol populations, and therefore we have increased the target screening n to 468, with a very conservative assumption of 2 subjects screened for every 1 enrolled, for a target sample of N=234 and n=117 per arm, which increases the projected power to 0.90.

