10.0 Statistical and Cost Effectiveness Analysis

Preliminary analyses of balance: balance across the study on potentially prognostic baseline variables will be appraised using analyses of variance for continuous variables and log-linear models for discrete and ordinal responses. Variables for which significant differences were observed will be included as covariates in later analyses. Sometimes variables with strong clinical associations with the primary outcome are identified post hoc, and usually included in the analysis to reduce bias and improve efficiency (yielding smaller p-values and narrower CIs). Further, in mixed models there is always a possibility that an analysis will not converge. This danger is minimized by including in the model only essential covariates. Hence, before analyzing the primary outcome measure, the plan is to determine which predictive variables rise to a sufficient level of importance.

10.1 Hypothesis 1: The rate of the primary good clinical outcome will be approximately twice as high among participants receiving XR-NTX compared with those receiving O-NTX. (Primary Aim, Treatment Effectiveness: To evaluate the effectiveness of XR-NTX vs. O-NTX in producing a primary good clinical outcome defined as abstinence or moderate drinking (≤ 2 drinks/day, men; ≤ 1 drink/day, women; and ≤ 2 heavy drinking occasions/month), during the final 20 of 24 weeks of primary care-based Medical Management for alcohol dependence)

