The primary outcome measure of this study is a binary measure of success defined by abstinence or moderate drinking only, as measured by the TLFb, with drop-outs from MM and research-only assessments assumed to have resumed baseline rates of heavy drinking, and therefore defined as good clinical outcome failures. Our analytic approach will be an intention-to-treat comparison of all randomized participants (N=234). The analysis will utilize a logistic regression with an indicator variable for treatment and covariate terms for baseline potential prognostic indicators that are not stratified for at randomization, including AA ethnicity, lead-in abstinence, medication preferences, baseline drinking severity, in-trial specialty treatment involvement, clinical site, and OPRM1 genotype. If the coefficient of treatment is significant the null hypothesis of equal treatment effect is rejected. Odds ratios will be calculated to quantify the risk to treatment failure of significant predictors (Secondary Aim 2: Patient-Level Predictors of Effectiveness: To identify patient-level characteristics associated with effectiveness in both arms). To differentiate time to a good clinical outcome failure, we will use a "cure model." The form of a cure model is $H(t) = 1 - p + pS(t)$; where $H(t)$ is the probability of failure at a time greater than t , p represents the probability of failure, and $S(t)$ the distribution of time to failure, conditional on failure occurring. The parameters will be estimated based both on Kaplan Meier methods and parametrically. The equality of the values of p for the two treatment arms will be tested using a nonparametric likelihood ratio test. For the parametric test, a logistic will be used to model p and a Weibull survival distribution will be used to model time to failure, $S(t)$. Both allow the use of covariates, which will complement the above logistic regression approach.

As originally proposed, naltrexone appears most effective at reducing heavy drinking, as opposed to producing complete abstinence, and all traditional alcohol treatment trial clinical endpoints, including continuous drinking and heavy drinking variables, as well as the CDT biomarker, which is specific for heavy drinking, are of great interest, and will be reported in the primary publication from this trial. In addition, rates

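### The covariate set of the primary logistic model is not fixed in advance: section 10.0 allows data-driven selection without a threshold, and the list in section 10.1 is open-ended

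*Combined protocol and SAP*

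**What the plan says.** Section 10.1 analyses the binary good clinical outcome in all 234 randomised participants by logistic regression, with a treatment indicator and covariates. The decision rule is: "If the coefficient of treatment is significant the null hypothesis of equal treatment effect is rejected". Seven covariates are named: African American ethnicity, lead-in abstinence, medication preference, baseline drinking severity, in-trial specialty treatment involvement, clinical site and OPRM1 genotype. The list is introduced by the word 'including', so it is not closed.

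Section 10.0 describes three further ways in which data can shape the model:

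- Baseline imbalance: "Variables for which significant differences were observed will be included as covariates in later analyses".
- Association with the outcome: it notes that sometimes "variables with strong clinical associations with the primary outcome are identified post hoc, and usually included in the analysis", and gives smaller p-values among the benefits.
- Importance: before the primary analysis, the team will decide which predictors matter enough. No cut-off or candidate list is given, and nothing says that the decision is made blind to arm.

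Neither section says how the named list and the selection step relate to each other.

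Section 9.0 bases power on an unadjusted test. It assumes success rates of "approximately 20% in O-NTX participants and 40% in the XR-NTX arm", says "we anticipate power of 0.84 to detect a 20% absolute difference in the primary outcome based on the Fisher's exact test" with 100 per group, and sets a "target sample of N=234 and n=117 per arm, which increases the projected power to 0.90".

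**The concern.** A single coefficient decides the trial, so the model that yields it should be identifiable before anyone sees results by arm. Here two analysts could follow sections 10.0 and 10.1 faithfully, fit different models, and reach different sides of the significance threshold.

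Each route has its own weakness. In a randomised trial a significant baseline difference is a chance finding, so the imbalance rule picks covariates by luck rather than by prognostic value. Identifying outcome predictors requires outcome data, so doing it before the primary analysis gives no protection unless arm is concealed. The importance step has no criterion that a reader could check afterwards. At stake are the error rate of the primary test and a reader's ability to confirm that the reported model was the planned one.

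**Working it through.** **Inputs from the documents.** 117 per arm; 20% versus 40% success; stated power 0.84 (100 per arm) and 0.90 (117 per arm) by Fisher's exact test (section 9.0). Drop-outs count as failures and all 234 are analysed (section 10.1).

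**Assumptions.** Alpha is not stated; 0.05 two-sided is assumed. The documents give no covariate-outcome strengths and no selection thresholds, so ranges are shown.

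**1. The plan's own figure.** Exact power of the two-sided Fisher test, by enumerating all 2×2 tables, is 0.844 at 100 per arm and 0.901 at 117 per arm. Both stated figures are reproduced, and neither counts any gain from covariate adjustment.

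**2. Chance of a significant baseline imbalance.** For k independent tests at 5% the chance of at least one is 1 − 0.95^k.

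- k = 6: 1 − 0.7351 = 0.265
- k = 7: 1 − 0.6983 = 0.302

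The seven covariates named in section 10.1, or six without the in-trial one, motivate these values of k.

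**3. Effect of the selection rule.** Trials with 117 per arm were simulated from logit P(success) = a(arm) + Σ b_j X_j, with six independent standard normal covariates. Two were prognostic, with an odds ratio per SD of 1.3 (weak), 1.65 (moderate) or 2.2 (strong). Treatment was tested by a Wald test in logistic regression. The rules compared were:

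- no covariates;
- a fixed set (all six covariates);
- covariates with baseline p < 0.05 between arms;
- those plus covariates associated with the outcome at p < 0.05;
- the most favourable of the 2^6 = 64 covariate subsets.

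| Rule | Type I error at 20% (weak / moderate / strong) | Power, 20% vs 40% (weak / moderate / strong) |
|---|---|---|
| Unadjusted | 4.2% / 4.9% / 4.9% | 0.93 / 0.92 / 0.92 |
| Fixed set | 4.9% / 5.0% / 5.4% | 0.92 / 0.93 / 0.96 |
| Imbalance only | 4.6% / 4.5% / 4.3% | 0.93 / 0.92 / 0.93 |
| Imbalance plus outcome association | 4.5% / 4.8% / 5.2% | 0.93 / 0.93 / 0.96 |
| Most favourable subset | 7.0% / 10.2% / 11.0% | not relevant |

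Monte Carlo error is about one percentage point or less. Unadjusted power exceeds 0.90 because Fisher's test is conservative; the pooled z-test gives 0.921 at 117 per arm.

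**4. Other assumptions.** With seven covariates, four of them prognostic (log odds ratio 0.26 or 0.5 per SD), and a 30% null rate, the most favourable choice gave 9.0% and 12.2%, against 5.3% and 4.9% for a fixed list. With 8 candidates (4 prognostic) and 15 candidates (5 prognostic) at log odds ratio 0.5, mechanical use of both rules gave 5.0% and 5.8%, against 4.8% and 5.4% for a fixed list.

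**The case against.** The strongest reply is that the plan is better than its loosest sentence. The remark about post hoc variables reads as a comment on common practice. The actual commitment is to settle the important predictors before the primary analysis and to keep only essential ones, and section 10.1 names seven. Applied mechanically, the rules hold type I error at 4.5% to 5.8% across the runs above. All of this stands. It narrows the point but does not remove it: the plan supplies no mechanical rule, the named list is open, and settling predictors beforehand is not the same as settling them blind to arm.

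Four stronger readings are tempting, and the documents do not support them:

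- **The written rules themselves inflate type I error.** They do not; the 7% to 12% needs an analyst who chooses the most favourable model.
- **The power gain from adjustment is lost.** That is true only of selection on imbalance alone. The plan also names covariates and admits outcome-associated ones, and the stated 0.90 never relied on adjustment.
- **Scales added mid-trial could enter the model and exclude early participants.** Section 3.7 says of the trauma and PTSD screeners "We will pilot in all remaining new patients and existing active patients validated brief screeners", for prevalence and change over time. Nothing names them as covariates.
- **An investigator who knows the allocation will pick the model.** Section 3.9 says that a team member, whose name is removed, "along with our study statistician will conduct the analyses of the primary and secondary effectiveness outcomes". Section 12.6.3, however, assigns all analyses to the biostatistician. The trial is open-label, but who would make the choice is not established.

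**Conclusion.** The concern holds in a limited form. The primary model is partly pre-specified but not closed, and section 10.0 lets three data-driven steps alter it without a threshold or blinding to arm. The deciding p-value can therefore be moved by covariate choice within the wording of the plan.

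A fixed list keeps type I error near 5%, and mechanical use of the written rules does about the same. Unconstrained choice of the most favourable set could take it to about 7% to 12%, which is an upper bound and not a forecast. Selecting on imbalance alone gives essentially unadjusted power, about 0.92 to 0.93 against 0.92 to 0.96 for a fixed list, a loss of at most about 3 points. All simulated figures depend on a two-sided 5% level and on the assumed number, independence and strength of covariates.

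**What to change.** In section 10.0, delete the significance-based balance rule, the post hoc sentence and the importance step as routes into the primary model. Report baseline balance descriptively, without tests.

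In section 10.1, replace the open wording with a closed list of pre-randomisation covariates drawn from those already named, frozen before outcomes are examined by arm. In-trial specialty treatment involvement should leave the list because it arises after randomisation. Clinical site should be checked at the same time, since section 1.0 describes recruitment into a single clinic and the term may have no variation.

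Add that any model with later-chosen covariates is a labelled sensitivity analysis and cannot replace the primary p-value.

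The cost is a change of wording, with no new data or visits. The downside is that a strong predictor discovered later can enter only a sensitivity analysis.

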3.6 What predicts good clinical outcomes in XR-NTX vs. O-NTX treatment?

Baseline and longitudinal predictors of interest in naltrexone alcohol treatment efficacy and effectiveness trials include gender, ethnicity and mu opioid receptor genotype, pre-treatment abstinence, and ancillary alcohol behavioral treatment involvement. Female gender has been shown to be associated with increased nausea and diminished oral naltrexone adherence⁴⁰ and less overall treatment effect, including sub-group results from the pivotal Garbutt XR-NTX efficacy trial, and gender remains a stratification variable at randomization.²⁷

Naltrexone’s relative ineffectiveness in African American clinical trial sub-populations, including in the COMBINE trial,⁴¹ is possibly mediated by low rates of the Asp40 OPRM1 functional allele in persons of African descent, who are primarily Asn40 homozygous.⁴² This Asp40 (A118G, ‘G’ allele) OPRM1 functional single nucleotide polymorphism (SNP) has been shown to be associated with successful treatment with naltrexone.^{43,44} We will be able to determine prospectively whether this allele is associated with retention and treatment effectiveness in both arms, potentially representing one of the first studies to assess the impact of Asp40 on XR-NTX treatment outcomes, which we feel adds to this proposals significance and

innovative potential. This will be in partnership with [name] (consultant) and [name] lab at the University of Pennsylvania, which will perform the genotyping in this proposal.

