7.2 Screening and Randomization

At the baseline visit, informed consent will be obtained and eligibility confirmed by the research coordinator and study physician. A subsequent randomization/treatment visit will then be scheduled within a 2 week time period. Several factors may be associated with naltrexone treatment success/failure. We will stratify urn randomization by gender and recruitment status (in-clinic vs. community referrals). Stratifying further, however, yields increasingly smaller cells, given 117 per arm; AA ethnicity, medication preference (monthly injectable vs. daily oral), and lead-in (3-day) abstinence will be analyzed as a priori predictors of effectiveness. Randomization is the starting point of the study (day 1, week 1).

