If the trial is negative, what’s the purpose of Aim 2? It might be observed that, if an intervention is not effective, it is meaningless to estimate its cost-effectiveness. Therefore, it might appear that the scientific validity of Aims 1 and 2 are inter-dependent. However, in the event that Aim 1 produces negative results, we will employ the computer simulation developed for Aim 2 for a slightly different purpose. Rather than using the simulation to estimate the cost-effectiveness of XR-NTX versus O-NTX, we will instead use the simulation to ask “what is the minimum level of incremental effectiveness required for an intervention to deliver sufficient value?” so that Aim 2 remains scientifically relevant and useful for decision makers. For example, even if XR-NTX does not deliver significant improvements in effectiveness compared to O-NTX, we would use the simulation to infer what levels of incremental effectiveness would be necessary to deliver sufficient value, given particular assumptions about incremental costs. For example, if a new intervention cost \$100/month more than O-NTX, how many fewer heavy-drinking days would it need to reduce compared to O-NTX in order to deliver sufficient value (incremental cost-effectiveness ratio < \$100,000/QALY)? That way, simulation results can inform future trial design. This approach is detailed in our recent publication,⁹⁸ and is concordant with principles of value-of-information analysis.⁹⁹

10.3 Secondary Aim 2: Patient-Level Predictors of Effectiveness. The multivariate models described for Aim 1, while testing the main and subsidiary hypotheses, will also be used to identify patient characteristics associated with treatment success. We hypothesize a priori that there will be less robust effectiveness in both arms among women and African Americans, while pre-treatment abstinence, voluntary specialty alcohol treatment and Alcoholics Anonymous involvement (patients are not directly referred to ancillary treatment), and presence of the Asp40 OPRM1 SNP will be associated with treatment effectiveness. We also hypothesize that these positive associations will be more pronounced within the XR-NTX arm due to the sustained medication adherence following each injection. We note, however, that these analyses will be exploratory, as the study is not powered to carefully test these secondary hypotheses.

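### The primary logistic model leaves out the two randomisation strata, and as written it has no gender or arm-by-predictor term for the Aim 2 hypotheses assigned to it

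*Combined protocol and SAP*

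**What the plan says.** On allocation, Section 7.2 states "We will stratify urn randomization by gender and recruitment status (in-clinic vs. community referrals", and Section 3.6 confirms that "gender remains a stratification variable at randomization".

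Section 10.1 specifies a logistic regression with one treatment indicator and "covariate terms for baseline potential prognostic indicators that are not stratified for at randomization". It names seven: African American ethnicity, lead-in abstinence, medication preference, baseline drinking severity, in-trial specialty treatment, clinical site and OPRM1 genotype. Neither stratification factor is listed, and no interaction is written.

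The opening of Section 10.0 gives two data-driven routes for further covariates. One is a balance test: "Variables for which significant differences were observed will be included as covariates in later analyses". The other is a screen for important predictors, with no threshold.

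Section 10.3 says the multivariate models of Aim 1 "will also be used to identify patient characteristics associated with treatment success". It hypothesises "less robust effectiveness in both arms among women and African Americans". It expects pre-treatment abstinence, specialty treatment or AA involvement, and the Asp40 allele to go with success, and adds that "these positive associations will be more pronounced within the XR-NTX arm". It also says that "these analyses will be exploratory, as the study is not powered to carefully test these secondary hypotheses".

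**The concern.** There are two mismatches. First, the trial balances its arms on gender and recruitment status and then bars those same factors from the primary model, so the analysis does not reflect the design. The plan's own reasoning points the other way. Section 7.2 introduces the strata as factors that may bear on treatment success, and Section 10.0 says that adjusting for prognostic variables improves efficiency.

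Second, Section 10.3 hands the Aim 1 models questions that the logistic model cannot answer. A model without a gender term gives no gender estimate. A model with main effects only forces each predictor's association to be equal in both arms, so it cannot show whether an association is stronger under XR-NTX. With no model prespecified for these hypotheses, the choice would be made with the data in hand.

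A related inconsistency is that clinical site is a covariate while the documents disagree on the number of sites.

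**Working it through.** **1. The plan's own power.** Inputs from Section 9.0: 20% vs 40%, Fisher's exact test, 100 and then 117 per arm. Two-sided alpha of 0.05 is assumed because the section states none. Exact enumeration gives 0.844 at 100 per arm (stated 0.84) and 0.901 at 117 (stated 0.90). Both reproduce. This test uses no covariates, so the strata do not affect it.

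**2. Cost of omitting the strata.** The documents give no stratum prevalences, stratum effects or urn parameters. Assumed: women 20-40%, community referrals 30-70%, stratum odds ratios 1 to 3 (reciprocal for gender), and a UD(1,1) urn within the four gender-by-recruitment cells. With N = 234 and 20,000 simulated trials per scenario, treatment was tested by a logistic Wald test. Marginal rates were 30/30 for type I error and 20/40 for power.

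| | Strata omitted | Strata included |
|---|---|---|
| Type I error | 4.1-5.1% | 4.8-5.2% |
| Power | 0.918-0.930 | 0.919-0.943 |

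The loss is about 0 to 1.6 points, and about 0 to 0.3 at odds ratios of 1.5 or less. Monte Carlo SE is about 0.15 points for type I error and 0.19 for power.

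A separate simulation (4,000 trials per cell, 30% women, 50% community, strata exactly balanced, no other covariates) gave:

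| Stratum odds ratio | Power, omitted | Power, included |
|---|---|---|
| 1 | 0.918 | 0.920 |
| 1.5 | 0.926 | 0.930 |
| 2 | 0.927 | 0.934 |
| 3 | 0.934 | 0.945 |

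With five further covariates of assumed strength in both models (10,000 trials per scenario), the loss is 0 to 1.4 points. Type I error is then 4.9-5.2% omitted and 5.1-5.7% included (SE about 0.22 points).

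**3. Shift in the odds ratio.** Unadjusted, 20% vs 40% gives (0.40/0.60)/(0.20/0.80) = 2.67. With the strata in the model the median is 2.7-3.0, because the odds ratio is then conditional on them.

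**4. Could the balance rule bring the strata in?** In 20,000 allocations, a two-sided 5% test flags a given stratum factor about 0.1% of the time under the UD(1,1) urn, against about 5% under simple randomisation. Looser urns raise this to 0.3-0.5% for UD(10,1) and about 2% for UD(50,1). The rule will almost never add the strata.

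**5. What an interaction term could show.** For gender, suppose men go from 20% to 40% and women stay at 20%, with 30% women. Each arm then has 117 × 0.7 = 81.9 men and 117 × 0.3 = 35.1 women.
- Difference in log odds ratios: ln(2.67) − 0 = 0.981.
- Variance, the sum of 1/[n p(1−p)] over the four cells: 1/(81.9 × 0.16) + 1/(81.9 × 0.24) + 2/(35.1 × 0.16) = 0.0763 + 0.0509 + 0.3561 = 0.483, so SE = 0.695.
- Power: Φ(0.981/0.695 − 1.96) = Φ(−0.55) = 0.29.

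At 20%, 40% and 50% women, power is 0.23, 0.33 and 0.35. For one treatment-by-predictor term in general (predictor prevalence 15-50%, predictor odds ratio 1 or 1.5 in the O-NTX arm), power is 13-21% for a ratio of odds ratios of 2 and 26-44% for 3. The 95% interval multiplies or divides that ratio by about 3.2-5.2.

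**6. Hypotheses against the logistic model.**

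| Section 10.3 hypothesis | Term needed | In the Section 10.1 logistic model? |
|---|---|---|
| Weaker effectiveness in women | Gender | No, excluded by the covariate rule |
| Weaker effectiveness in African Americans | Ethnicity | Yes |
| Positive associations stronger under XR-NTX | Arm-by-predictor | No |

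**7. Sites.** The study overview describes one primary care site. Section 3.8 refers to two proposed settings, and Sections 7.4 and 8.2 are worded for two facilities. With one site, the site covariate is a constant and cannot be estimated.

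**The case against.** The strongest reply is that little is at stake. The power loss nears 1.6 points only at assumed odds ratios of 3, and the documents support no such value. Once other covariates are in the model, omitting the strata is about neutral for type I error rather than conservative, and adding them nudges it to 5.1-5.7%. The fix also spends degrees of freedom. About 117 × 0.2 + 117 × 0.4 = 70 successes are expected. Treatment, seven covariates and two strata make ten terms, or about seven successes per term, against 70/8, or nearly nine, now. All of this stands and limits the weight of the strata point. It does not justify a rule that singles out the design factors for exclusion.

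On Aim 2, Section 10.3 refers to models in the plural. The cure model allows covariates, and the repeated-measures model has terms for baseline variables. Neither carries the restriction, so gender could enter either one. That is fair: gender is not shut out of the whole plan. But neither model names gender or recruitment status, and no interaction with a predictor is written anywhere. Separate fits by arm could supply part of the answer, but none is specified.

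Finally, the plan itself calls these analyses exploratory and unpowered. That bears on how results may be read. It does not remove the need to define the model for hypotheses stated in advance.

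**Conclusion.** The concern holds. The covariate rule in Section 10.1 excludes exactly the two factors used to stratify. The logistic model also lacks the terms needed for the gender and between-arm hypotheses of Section 10.3. The harm to the primary test is small: about 0 to 1.6 points of power, with type I error slightly low without other covariates and about nominal with five. These figures rest on assumed prevalences, stratum effects and urn parameters. The stated power of 0.90 and the sample size stand. The more important consequence is that the Aim 2 hypotheses have no prespecified estimate. Closing that gap gives defined estimates with wide intervals, not confirmatory answers. The change should be made, but the primary comparison does not depend on it.

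**What to change.** - **Primary model.** Delete the clause in Section 10.1 that limits covariates to non-stratified factors, and add gender and recruitment status as prespecified terms. Note that the conditional odds ratio will shift slightly.
- **Aim 2.** Prespecify a separate exploratory logistic model with main effects for gender and African American ethnicity. Add treatment-by-predictor terms one at a time for pre-treatment abstinence, specialty treatment or AA involvement, and Asp40 OPRM1. Report estimates with 95% intervals and state that power is low. Specialty treatment or AA involvement includes involvement that begins during the trial, so report its term as descriptive only.
- **Sites.** Reconcile the one-site and two-site wording. If there is one site, drop clinical site from the covariates, which leaves nine terms and about 70/9 = 7.8 expected successes per term.

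The cost is wording in the analysis plan. Both strata are known at randomisation and the Aim 2 predictors are already collected, so sample size, visits and procedures do not change.

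### Aim 2 takes its African American odds ratio from a model that also adjusts for OPRM1 genotype, a possible mediator of that difference, so it estimates only the part that Asp40 does not explain

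*Combined protocol and SAP*

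**What the plan says.** Section 10.3 states as a prior expectation that "there will be less robust effectiveness in both arms among women and African Americans", and separately that "presence of the Asp40 OPRM1 SNP will be associated with treatment effectiveness". It sets up no model of its own for these questions. The multivariate models of Aim 1 "will also be used to identify patient characteristics associated with treatment success".

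The Aim 1 model is the logistic regression in section 10.1. It has a treatment indicator and covariate terms, "including AA ethnicity, lead-in abstinence, medication preferences, baseline drinking severity, in-trial specialty treatment involvement, clinical site, and OPRM1 genotype". The same section ties Aim 2 to that fit: "Odds ratios will be calculated to quantify the risk to treatment failure of significant predictors".

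Section 3.6 gives the reason for interest in the genotype. Naltrexone's weaker performance in African American trial sub-populations "is possibly mediated by low rates of the Asp40 OPRM1 functional allele in persons of African descent, who are primarily Asn40 homozygous".

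Section 7.2 lists African American ethnicity among the a priori predictors but describes no other model for it. The plan contains no fit without genotype, no sequential fit and no mediation analysis. Section 10.3 calls these analyses exploratory and says the study is not powered for them.

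**The concern.** The hypothesis concerns an overall difference: do African American participants do less well on naltrexone? A model containing both ethnicity and genotype answers a narrower question: do they do less well than other participants of the same genotype? If Asp40 lies on the path from ethnicity to outcome, as section 3.6 suggests it may, adjusting for it removes the part of the difference that runs through it.

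What is at stake is how an a priori hypothesis is reported. An adjusted odds ratio near 1 could be written up as no difference by ethnicity in the very situation where African American participants do worse for the reason the protocol proposes. A larger sample would not cure this, because the mismatch lies in the quantity estimated.

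**Working it through.** **The plan's own figures.** No figure is given for Aim 2. The only power figures are in section 9.0: 0.84 at 100 per group and 0.90 at 117 per group, Fisher's exact test, 20% versus 40%. Full enumeration, assuming two-sided alpha 0.05 (not stated there), gives 0.844 and 0.901, so both reproduce.

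**Inputs for this point.** From the documents: N = 234 (section 9.0), and 15% African American in the pilot (section 3.8), so 0.15 × 234 = 35.1, about 35 people. Assumed, because the documents give no values: Asp40 carriage of 2-5% in African Americans and 30-40% in others; success of 50-60% in carriers and 25% in non-carriers; no effect of ethnicity except through carriage (full mediation).

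**Overall odds ratio.** Success in a group = carrier rate × carrier success + (1 − carrier rate) × non-carrier success.

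- Largest difference (2%, 40%, 60%): African American 0.02 × 0.60 + 0.98 × 0.25 = 0.257; others 0.40 × 0.60 + 0.60 × 0.25 = 0.390. Odds ratio (0.257/0.743) / (0.390/0.610) = 0.54.
- Smallest difference (5%, 30%, 50%): African American 0.05 × 0.50 + 0.95 × 0.25 = 0.2625; others 0.30 × 0.50 + 0.70 × 0.25 = 0.325. Odds ratio (0.2625/0.7375) / (0.325/0.675) = 0.74.

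**Genotype-adjusted odds ratio.** Within each genotype the two groups have the same success rate by assumption, so the odds ratio is 1.00. This restates full mediation and is not an independent result. About 35 × 0.02 to 35 × 0.05 = 0.7 to 1.75 African American carriers would be expected, so the adjusted contrast is made almost entirely among non-carriers.

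**Simulation at N = 234.** Logistic models with arm (20% versus 40%) and ethnicity were fitted with and without genotype, 800 runs per scenario. Assumed ranges: African American share 15-50%, carriage 3-8% versus 25-40%, genotype odds ratio 2-5. The partial-mediation rows use carriage of 5% versus 30%, a genotype odds ratio of 3 and an added direct ethnicity odds ratio of 0.6.

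| Scenario | Model | Median ethnicity odds ratio | Rejection rate at 0.05 |
|---|---|---|---|
| Full mediation | with genotype (as planned) | 0.96-1.03 | 3.4-5.9% |
| Full mediation | without genotype | 0.52-0.91 | 5-55% |
| Partial mediation | with genotype | 0.56-0.61 | 16-35% |
| Partial mediation | without genotype | 0.42-0.45 | 40-75% |

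Under full mediation the planned model rejects at about the alpha rate. Under partial mediation the estimate is attenuated but does not vanish.

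**Power of the model without genotype.** For 35 versus 199 participants over the grid of assumptions above, exact enumeration of a simple two-group comparison at two-sided 0.05 gives power of 12-35% by likelihood-ratio test and 9-31% by Wald test.

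**The case against.** The other side has several good points.

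- **The mechanism is offered only as a possibility.** A reader might infer that the protocol asserts that genotype carries the ethnic difference, and hence that its own hypothesis must come out null. The text does not go that far. Section 3.6 says possibly, section 10.3 names Asp40 separately from the ethnicity hypothesis, and an expected odds ratio of 1 needs complete mediation by a single SNP. This stands, and the point is conditional for that reason.
- **Aim 2 is exploratory.** A reader might infer that the plan would refute its hypothesis. A non-significant coefficient in an analysis declared exploratory and unpowered refutes nothing. This stands and limits the weight of the point. It does not make the estimate match the hypothesis.
- **The model without genotype would usually be non-significant too.** With power of 9-35% on the grid, this is right. What remains is the choice of quantity to estimate.
- **The covariate list may be trimmed.** Section 10.0 keeps only covariates judged important enough, so joint entry is not certain. But nothing says genotype would be dropped for the ethnicity question, and if Asp40 predicts outcome as hypothesised, it is likely to be kept.
- **A jointly adjusted model is ordinary practice, and the hypothesis does not say which difference is meant.** Separating the two effects is a fair second question, and the Asp40 coefficient would still show part of the mechanism. But the hypothesis is worded about African Americans as a group, with no condition on genotype, and the plan has no estimate of that overall difference.

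**Conclusion.** The point holds in a limited form. As planned, the African American odds ratio estimates the difference that Asp40 does not explain, while section 10.3 hypothesises the overall difference. Under the assumed carrier and success rates and full mediation, the two are 1.00 and 0.54-0.74. Under partial mediation with a direct odds ratio of 0.6, they are about 0.56-0.61 and 0.42-0.45. The sizes rest on assumptions. The direction needs only that the mechanism suggested in section 3.6 operates at least in part.

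Two further inferences are not supported. The primary treatment comparison is not shown to be biased by this, since ethnicity and genotype are both baseline variables. Nor does the missing model explain any lack of significance by itself: power for the ethnicity contrast is low with or without genotype. This is a cheap correction to a declared secondary hypothesis and does not threaten the trial's main conclusion.

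**What to change.** In section 10.3:

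1. Estimate the African American association from the section 10.1 model without OPRM1 genotype, and base the a priori hypothesis on that odds ratio with its confidence interval. Because the hypothesis is stated for both arms, also report the ethnicity-by-arm interaction from this model.
2. Then add OPRM1 genotype and report both ethnicity estimates and the change between them, labelled as the exploratory mediation question.
3. State that a genotype-adjusted odds ratio near 1 will not be reported as absence of an ethnic difference.

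The cost is one extra model fit on data already being collected and a few sentences in the SAP. The analysis stays exploratory.
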